# 10.9 Safety Stopping/Holding Rules

Safety holding rules have been developed considering the fact that this is a first-in-human study.

### 10.9.1 Group holding rules (applies to Groups 1 and 2/3)

If a holding rule is activated, then further vaccinations in the group (Group 1 and/or Group 2/3) will not occur until an internal safety review has been conducted and it is deemed appropriate to restart dosing. Note that as Groups 2 and 3 will be recruited in parallel, if a group holding rule is activated for one of the two groups, then further vaccinations in both groups would go on hold. The regulatory authority must be informed of the hold via substantial amendment and a request

to restart dosing with pertinent data must be submitted as a further, subsequent substantial amendment. The internal safety review will consider:

- The relationship of the AE or SAE to the vaccine.
- The relationship of the AE or SAE to the vaccine dose, or other possible causes of the event.
- If appropriate, additional screening or laboratory testing for other volunteers to identify those who may develop similar symptoms, and alterations to the current Participant Information Sheet (PIS) are discussed.
- New, relevant safety information from ongoing research programmes on the various components of the vaccine (i.e. the Matrix-M adjuvant).

The local ethics committee and adjuvant manufacturers (Novavax) will also be notified if a holding rule is activated or released to ensure that each Party is obliged to comply with the performance and activities related to the clinical trial (there is a confidential Safety Data Exchange Agreement, SDEA, in place). All vaccinated volunteers will be followed for safety until resolution or stabilisation (if determined to be chronic sequelae) of their AEs. Novaxax will be provided with SAE and pregnancy reports and any safety concerns causing a suspension as per the SDEA beween Oxford and Novavax

The group holding rules are as follows:

#### Solicited local AEs:

 If two or more doses of a vaccine are followed by a Grade 3 solicited local AE beginning within 2 days after vaccination (day of vaccination and one subsequent day) and persisting at Grade 3 for > 72 hrs.

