#### 10.1.6 Foreseeable Adverse Reactions

The foreseeable ARs following vaccination with Pfs48/45 in Matrix-M adjuvant are: injection site pain, erythema, warmth, swelling, pruritus, myalgia, arthralgia, headache, fatigue, fever, feverishness, malaise and nausea. These AEs will be listed as 'solicited AEs' providing they occur within 7 days of the day of vaccination. 'Unsolicited AEs' are AEs other than the foreseeable ARs occurring within the first 7 days, or any AEs occurring after the first 7 days after vaccination.

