### Solicited systemic AEs:

 If two or more doses of a vaccine are followed by a Grade 3 solicited systemic AE beginning within 2 days after vaccination (day of vaccination and one subsequent day) and persisting at Grade 3 for > 48 hrs.

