### • Unsolicited AEs:

- o If two or more volunteers develop a Grade 3 unsolicited AE (including the same laboratory AE) that is considered possibly, probably or definitely related to vaccination.
- However, if a study participant has a Grade 3 unsolicited (or laboratory) AE considered 'possibly' related to vaccination which persists at Grade 3 < 48 hours that, in the opinion of the Investigator, is of non-clinical significance and where a different cause is judged as likely, the event will not be counted as part of the group holding AEs.

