# • A serious AE considered possibly, probably or definitely related to vaccination occurs

# 10.9.2 Individual stopping rules

In addition to the above stated group holding rules, stopping rules for individual volunteers will apply (i.e., indications to withdraw individuals from further vaccinations).

• Local reactions: Injection site ulceration, abscess or necrosis.

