#### Laboratory AEs:

 The volunteer develops a Grade 3 laboratory AE considered possibly, probably or definitely related within 7 days after vaccination and persisting continuously at Grade 3 for >72hrs.

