# Solicited systemic AEs:

 The volunteer develops a Grade 3 systemic solicited AE considered possibly, probably or definitely related within 2 days after vaccination (day of vaccination and one subsequent day) and persisting continuously at Grade 3 for >72hrs.

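### Related, prolonged, non-serious Grade 3 listed reactions first appearing on days 2-6 meet no count-based group holding rule

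*Combined protocol and SAP*

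**What the plan says.** Section 10.9.1 has four group holding rules.

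- **Solicited local:** two or more doses "followed by a Grade 3 solicited local AE beginning within 2 days after vaccination (day of vaccination and one subsequent day"), lasting at Grade 3 for more than 72 hours.
- **Solicited systemic:** two or more doses "followed by a Grade 3 solicited systemic AE beginning within 2 days after vaccination (day of vaccination and one subsequent day"), lasting at Grade 3 for more than 48 hours.
- **Unsolicited:** "If two or more volunteers develop a Grade 3 unsolicited AE (including the same laboratory AE"), provided the event is at least possibly related. There is no onset window and no minimum duration. A short carve-out covers some possibly related events lasting under 48 hours.
- **Serious:** "A serious AE considered possibly, probably or definitely related to vaccination occurs".

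Section 10.1.6 decides which rule a listed reaction falls under. The listed reactions are solicited "providing they occur within 7 days of the day of vaccination". Unsolicited events "are AEs other than the foreseeable ARs occurring within the first 7 days, or any AEs occurring after the first 7 days after vaccination".

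Two individual stopping rules in section 10.9.2 are relevant. The systemic one applies when the volunteer "develops a Grade 3 systemic solicited AE considered possibly, probably or definitely related within 2 days after vaccination", with the same day 0-1 definition. The laboratory one applies to anyone who "develops a Grade 3 laboratory AE considered possibly, probably or definitely related within 7 days after vaccination and persisting continuously at Grade 3", with a threshold of more than 72 hours.

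Section 10.2 requires a causality assessment for unsolicited AEs, and separately for SAEs, but not for non-serious solicited AEs. Section 10.8 lets the LSM, CI, sponsor or ethics committee put the study on hold for any event they judge unsafe.

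**The concern.** A holding rule fixes in advance when dosing pauses, and section 10.9 says these rules were written with a first-in-human study in mind. Here the onset windows and the AE definitions do not meet. The solicited rules stop looking after day 1, and the unsolicited rule does not admit a listed reaction until the solicited period ends. Two or more related, prolonged Grade 3 reactions starting in between would trigger no predefined pause. The decision would rest on individual judgement, although the same events starting earlier or later could trigger a hold.

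Doubt about attribution does not explain the pattern. If later onset were thought too weakly linked to vaccine, day 8 would be a poorer candidate than day 3, yet a related day-8 reaction can count.

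**Working it through.** The documents give no operating characteristics for the holding rules, so there is no figure to reproduce. The check has two parts.

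**1. Mapping by day of first onset.** Take two volunteers, each with one non-serious, probably related Grade 3 listed reaction lasting 96 hours. That exceeds both duration thresholds.

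| First onset | Class under 10.1.6 | Group rule met |
|---|---|---|
| Day 0-1 | Solicited | Solicited local or systemic rule (two of the same type) |
| Day 2-6 | Solicited | None |
| Day 7, solicited period read as days 0-7 | Solicited | None |
| Day 7, solicited period read as days 0-6 | Unsolicited | Unsolicited rule |
| Day 8 onward | Unsolicited | Unsolicited rule |

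Uncovered onset days: 7 - 2 = 5 of 7, or 8 - 2 = 6 of 8. Section 10.1.6 does not settle which. Section 9.3.3 starts the unsolicited diary on day 7, which is why that day is ambiguous.

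**2. Extra holds if later onset counted.** Inputs: up to 10 volunteers per group and three doses each (sections 7.3 and 11.1), so n = 10 x 3 = 30 doses in Group 1. Section 10.9.1 holds Groups 2 and 3 together, so n = 20 x 3 = 60. The per-dose rate p of a qualifying late-onset reaction is an assumption; the documents give none. Doses are treated as independent and Groups 2/3 are counted together. Under the present text these events alone trigger a count-based hold with probability 0 at any p. With the change:

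P(X >= 2) = 1 - (1-p)^n - n p (1-p)^(n-1).

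For n = 30, p = 0.01: 1 - 0.7397 - 0.2242 = 0.0361.
For n = 60, p = 0.01: 1 - 0.5472 - 0.3316 = 0.1212.

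| p per dose | Group 1, n = 30 | Groups 2/3, n = 60 |
|---|---|---|
| 0.25% | 0.26% | 1.00% |
| 0.5% | 0.99% | 3.65% |
| 1% | 3.61% | 12.12% |
| 2% | 12.05% | 33.81% |

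At the minimum size of 8 per group (n = 24 and 48), p = 0.25%, 0.5% and 1% give 0.17%, 0.64%, 2.39% and 0.65%, 2.42%, 8.34%. Because p combines local and systemic reactions while the rules count them separately, these figures are upper bounds for two late events of the same type.

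One early and one late event could also make up the two. If early qualifying events occur at the same rate p, the added chance is P(Bin(n, 2p) >= 2) - P(Bin(n, p) >= 2). At p = 1% and n = 30 this is 12.05% - 3.61% = 8.44%; at n = 60 it is 33.81% - 12.12% = 21.69%. At p = 0.25% and 0.5% it is 0.73% and 2.62% (n = 30), and 2.65% and 8.47% (n = 60).

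**The case against.** The short window looks deliberate. It is spelled out in three rules, and the Modification History records that the group holding wording was changed at the regulator's request, without saying which words. The solicited group rules have no relatedness test, so early onset does that work. This stands as a reason to leave the day 0-1 rules alone. It does not explain why a related reaction is excluded on day 3 and admitted on day 8.

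The case is also narrow. It needs first onset in the gap, Grade 3, long duration, relatedness, no seriousness and at least two occurrences. A reaction that starts mildly on day 0-1 and reaches Grade 3 later can be read as covered. Section 7.6.2 expects mostly mild to moderate, transient reactions. Severe hypersensitivity is reported as an SAE (section 10.6), and one related SAE holds the group. All of this stands and lowers the severity.

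A reader might infer that such reactions would go unseen. The documents do not support that:

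- e-diaries are reviewed daily for 7 days for the first eight Group 1 volunteers (section 7.4.2);
- the first three volunteers in Groups 1 and 2 have 48-hour reviews at each dose (sections 7.3 and 7.4.1);
- a formal review of 7-day data precedes escalation (sections 7.4.1 and 7.4.2);
- every dose is followed by a day-7 visit with diary review (sections 9.3.3, 9.3.5 and 9.3.7).

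But none of these is an event-triggered hold, and neither the daily review nor the pre-escalation review reaches the 50 µg doses in Groups 2/3.

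Finally, a reader might assume that a relatedness condition alone would keep intercurrent illness out of an extended rule. It would not. Table 3 in section 10.2 rates an event as possible on any one of three criteria, including resemblance to reactions seen with other vaccines. Fever or myalgia from a viral illness on day 3 could qualify. The carve-out in the unsolicited rule would not help, because it covers only events under 48 hours. An extension therefore needs its own exception.

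**Conclusion.** The gap is real and follows from the text: related, non-serious Grade 3 listed reactions that first start on days 2-6 (day 7 depending on the reading) and last more than 72 hours (local) or 48 hours (systemic) meet no count-based group rule. Confidence in this is high.

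Severity is minor; this is a cheap tightening. Five of seven, or six of eight, uncovered days might be taken to mean that most of the risk is uncovered. Those are counts of days; the documents give no onset distribution and nothing to suggest that late, prolonged Grade 3 reactions are expected.

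Nor do the documents clearly show that the affected volunteer would go on being vaccinated. The individual systemic rule repeats the day 0-1 window, but the first item under the unsolicited heading in section 10.9.2 refers to any related Grade 3 AE lasting over 72 hours and may apply if read without its heading. That part stays uncertain. The hold probabilities rest wholly on the assumed p.

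**What to change.** Keep the day 0-1 rules unchanged and make four text edits.

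1. **Solicited local group rule (10.9.1):** also count towards the two doses any Grade 3 solicited local AE that begins after day 1 but within 7 days of the vaccination day, lasts more than 72 hours at Grade 3 and is at least possibly related. Do not count an event rated only possibly related where a different cause is judged likely, for example a confirmed infection such as COVID-19.
2. **Solicited systemic group rule (10.9.1):** the same addition and exception, with more than 48 hours.
3. **Individual systemic rule (10.9.2):** widen the onset window to within 7 days of the vaccination day, with the same exception. Keep the 72 hours and the existing relatedness condition. The individual laboratory rule already takes this form.
4. **Causality (10.2):** require causality to be assigned for these events when the duration threshold is reached, rather than waiting for a planned review.

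Using the time limit of section 10.1.6 means that a related day-7 reaction falls under either the amended rules or the unsolicited rule on both readings. One small difference remains: the unsolicited rule has no matching exception for events lasting beyond 48 hours.

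The diary, visit and follow-up data are already collected, so the added work is an amendment and a few causality assessments. The main downside is the somewhat higher chance of a temporary hold shown in the working. A hold needs one substantial amendment to report it and another to restart. It stops Groups 2 and 3 together (section 10.9.1), and could push second or third doses outside the -7/+14 day window in Table 2.

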### Solicited systemic AEs:

 If two or more doses of a vaccine are followed by a Grade 3 solicited systemic AE beginning within 2 days after vaccination (day of vaccination and one subsequent day) and persisting at Grade 3 for > 48 hrs.

### • Unsolicited AEs:

- o If two or more volunteers develop a Grade 3 unsolicited AE (including the same laboratory AE) that is considered possibly, probably or definitely related to vaccination.
- However, if a study participant has a Grade 3 unsolicited (or laboratory) AE considered 'possibly' related to vaccination which persists at Grade 3 < 48 hours that, in the opinion of the Investigator, is of non-clinical significance and where a different cause is judged as likely, the event will not be counted as part of the group holding AEs.

# • A serious AE considered possibly, probably or definitely related to vaccination occurs

# 10.9.2 Individual stopping rules

In addition to the above stated group holding rules, stopping rules for individual volunteers will apply (i.e., indications to withdraw individuals from further vaccinations).

• Local reactions: Injection site ulceration, abscess or necrosis.

#### Laboratory AEs:

 The volunteer develops a Grade 3 laboratory AE considered possibly, probably or definitely related within 7 days after vaccination and persisting continuously at Grade 3 for >72hrs.

# Solicited systemic AEs:

 The volunteer develops a Grade 3 systemic solicited AE considered possibly, probably or definitely related within 2 days after vaccination (day of vaccination and one subsequent day) and persisting continuously at Grade 3 for >72hrs.

#### Unsolicited AEs:

- The volunteer has a Grade 3 AE, considered possibly, probably or definitely related to vaccination, persisting continuously at Grade 3 for >72hrs.
- The volunteer has an acute allergic reaction or anaphylactic shock following the administration of the vaccine investigational product.

### A serious AE considered possibly, probably or definitely related to vaccination occurs

# 10.10 Contraception and pregnancy

Volunteers with the potential to become pregnant are defined as those who are fertile and able to become pregnant following menarche until becoming post-menopausal, unless permanently sterile. A post-menopausal state is defined as no menstruation for 12 months without a known cause.

Volunteers with the potential to become pregnant are required to use an effective form of contraception during the course of the study as this is a Phase I, first-in-human, study and there is currently no information about the effect of this vaccine on a foetus.

Acceptable forms of contraception for volunteers with the potential to become pregnant are:

- Established use of oral, injected or implanted hormonal methods of contraception.
- Placement of an intrauterine device or intrauterine system.
- Male sterilization: if the vasectomised partner is the sole partner for the participant.
- True abstinence from sex with sperm-producing partners, when this is in line with the preferred and usual lifestyle of the participant (periodic abstinence and withdrawal are not acceptable methods of contraception).

Pregnancy, lactation or intention to become pregnant during the study is an exclusion criteria.

#### 11 STATISTICS

## 11.1 Sample size

This is an observational and descriptive safety study, where healthy adult volunteers living in the UK will be vaccinated with Pfs48/45, in formulation with the Matrix-M adjuvant. Up to a total of 30 volunteers across three equally divided groups will be vaccinated. Each volunteer will receive three doses of Pfs48/45, formulated in 50 µg Matrix-M, on days 0, 28 and 56 (see Table 2 for exact dosing regimen depending on group allocation). This sample size should allow estimation and comparison of the frequency and magnitude of the outcome measures, at and between the three different dosing regimens. As this is the first study involving the Pfs48/45 in Matrix-M vaccine, there is no available data to enable more precise modelling/power calculations. However, it is considered that eight to ten volunteers in each group will be sufficient to enable detection of statistically significant differences in the primary and secondary outcome measures (see Section 6) between the groups. Specifically, we will be able to assess the optimal dose for future studies based on the safety/tolerability as well as immunogenicity of each of the three dosing regimens.

### 12 QUALITY CONTROL AND QUALITY ASSURANCE PROCEDURES

### 12.1 Investigator procedures

Approved site-specific SOPs will be used at all clinical and laboratory sites.

### 12.2 Monitoring

Monitoring will be performed by Appledown external monitors using established procedures, according to the principles of Good Clinical Practice (GCP). Following written SOPs, the monitors will verify that the clinical trial is conducted and data are generated, documented and reported in compliance with the protocol and GCP. The site will provide direct access to all trial-related source data/documents and reports for the purpose of auditing by the Sponsor and inspection by local and regulatory authorities.

### 12.3 Modification to protocol

No amendments to this protocol will be made without consultation with, and the agreement of, the Sponsor. Any amendments to the trial that become necessary during the course of the trial must be discussed by the Investigator and Sponsor concurrently. If agreement is reached concerning the need for an amendment, it will be produced in writing by the CI and will be made a formal part of the protocol following ethical and regulatory approval, as applicable.

An administrative change to the protocol is one that modifies administrative and logistical aspects of a protocol but does not affect the participant's safety, the objectives of the trial and its progress. An administrative change may not require UK ethical committee approval; however, the REC will be notified in the event of any such change.

The Investigator is responsible for ensuring that changes to an approved trial, during the period for which ethical committee(s) approval has already been given, are not initiated without review and approval from the ethics committee(s) and regulatory authorities except to eliminate apparent immediate hazards to the participant (Urgent Safety Measures only). Protocol adherence is a fundamental part of the conduct of a clinical study. Changes to the approved protocol need prior approval unless for urgent safety reasons. Investigators must not request a protocol waiver to enter a patient who does not satisfy the selection criteria.

### 12.4 Protocol deviation

Any deviations from the protocol will be documented in a protocol deviation form and filed in the TMF.

#### 12.5 Audit & inspection

The Quality Assurance manager performs systems-based internal audits to check that trials are being conducted, data recorded, analysed and accurately reported according to study protocols, departmental SOPs and in compliance with GCP. The audit schedule includes laboratory activities. The internal audits will supplement the independent monitoring process and will review processes not covered by the independent monitor.

The Sponsor, trial site, ethical committee(s), and authorised individuals may carry out audit to ensure compliance with the protocol, GCP and appropriate regulations. GCP inspections may also be undertaken by the regulatory authority to ensure compliance with protocol and national regulations. The Sponsor will assist in any inspections.

#### 12.6 Serious breaches

The Medicines for Human Use (Clinical Trials) Regulations contain a requirement for the notification of "serious breaches" to the MHRA within 7 days of the Sponsor becoming aware of the breach.

A serious breach is defined as "A breach of GCP or the trial protocol which is likely to effect to a significant degree –

- (a) the safety or physical or mental integrity of the participants of the trial; or
- (b) the scientific value of the trial.

In the event that a serious breach is suspected the Sponsor must be contacted within 1 working day. In collaboration with the CI the serious breach will be reviewed by the Sponsor and, if appropriate, the Sponsor will report it to the REC, regulatory authority and the relevant NHS host organisation within seven calendar days.

# 12.7 Publication policy

The Investigators will be involved in reviewing drafts of the manuscripts, abstracts, press releases and any other publications arising from the study. Authorship will be determined in accordance with the International Committee of Medical Journal Editors guidelines and other contributors will be acknowledged.

# 12.8 Intellectual Property

Ownership of intellectual property generated by employees of the University vests in the University. The protection and exploitation of any new intellectual property is managed by the University's technology transfer office, Oxford University Innovation.

#### 13 ETHICS

### 13.1 Declaration of Helsinki

The Investigator will ensure that this study is conducted according to the principles of the current revision of the Declaration of Helsinki 2008.

### 13.2 GCP guidelines

The Investigator will ensure that this study is conducted in full conformity to the Medicines for Human Use (Clinical Trials) Regulations 2004 (SI 2004 No. 1031) and its amendments and with the guidelines for GCP (CPMP/ICH/135/95) July 1996.

